## **PROCEDURE**

### **Phone Screening**

Potential participants will be recruited at participating Allegiance affiliated supermarkets using flyers and study ads printed on store receipts, or email messages. These materials will include contact information for the study. If a subject calls to express interest in participating in the study, a phone screening (**Appendix A**) will be conducted by the research coordinator or the study team. Alternatively, subjects may be screened by the research team in-person in the supermarket where the potential subject is shopping. This screening will be used to assess preliminary eligibility for the study. During screening, subjects will be asked to self-report their estimated height and weight. Subjects will also be asked to respond to questions relevant to the basic inclusion and exclusion criteria for the study as outlined in section 5b. We are requesting a waiver of signed consent for this phone and in-store screening. If participants report a BMI between 23.5 and 24.5, they will be invited for the screening visit as the likelihood of subjects underestimating their weight and/or overestimating their height is high.

### **Screening Visit (Duration: ~20 min)**

An in-person screening will be scheduled for qualified subjects (as evidenced by phone/in-store screening) at Mount Sinai Morningside/St. Luke's Hospital or Quest Diagnostics. Prior to this visit, subjects will fast overnight for a minimum of 12 hours. The written consent may be obtained in-person or virtually using REDCap and a secure hospital Zoom interface. In this instance, participants will be provided a copy of the consent form to download from REDCap and the study will be explained using a HIPAA-compliant Zoom account from the hospital. The participant will be asked to sign the consent form through REDCap. Consent forms may also be signed in person. Study details will be explained to participants followed by a short morning questionnaire. Subjects will then have their height and weight obtained in duplicate and their body temperature measured. Body weight will be assessed on a beam scale and body composition assessed using a Tanita scale based on bioelectrical impedance (BIA). Waist circumference over light clothing will be obtained in duplicate. Participants will be asked to provide, either in-person or virtually using REDCap and a secure Zoom interface, information on their past

	Protocol Name:	Multi-level supermarket discounts of fruits and vegetables on intake and health
	Principal Investigator:	[name]
	Primary Contact Name/Contact Info:	[name] [contact] [name] [contact]
	Date Revised:	8/7/20
	Study Number:	HS#: 16-00407 GCO#: 16-1050

medical history (Appendix M), and will fill out a Behavioral checklist questionnaire (Appendix D). Next, blood pressure readings will be made in duplicate. Blood will be drawn to screen for unknown diabetes (fasting glucose, HbA1C) and elevated lipid profile (total cholesterol, LDL, HDL, triglycerides). Electrolytes and liver function will also be measured as indicators of general health status. A urine sample will be collected and analyzed using the T-Cup TDOA-1144 14 Panel Urine Drug Screen for drug testing, as well as sent to Quest Diagnostics for female subjects < 55 y.o to confirm their non-pregnant status. The pregnancy test will only be repeated at subsequent study visits if there is unexplained weight gain or upon participant request.

#### Suicidality Inquiry and Follow-up Procedure

In the event that a subject responds affirmatively (“yes”) to screening questions related to suicidality and/or depression, they will be advised by study staff to seek counsel from a licensed psychologist from the Mount Sinai faculty practice trained to address depression and suicidality. In addition, study staff will be required to follow up with the subject twice thereafter – once to confirm an appointment was made and/or try to address any barriers to making an appointment and then again to confirm the subject attended their scheduled appointment with a licensed psychologist.

If subjects qualify based on the Screening Visit, an account will be created for the participant through Allegiance. Subjects will be asked to stop using their current Allegiance affiliated supermarket reward card after they will be provided with a new scan card at the next study visit time (Study Visit 1).

#### Study Visit 1; wk 0 (Duration: ~20 min)

After the results of the blood tests are reviewed, eligible subjects will be asked to come in for study visit 1. Prior to this visit, subjects will fast overnight for a minimum of 12 hours. Body temperature will be taken and a short Morning Questionnaire completed. Participants will also complete a Behavioral checklist (Appendix D), a F&V Liking assessment (Appendix F) as well as an Income questionnaire (Appendix B), either in-person or virtually using REDCap and a secure Zoom interface,. A small blood sample will be drawn and a general blood chemistry panel will be ordered (fasting glucose, protein bound glucose (fructosamine), lipid profile (total cholesterol, LDL, HDL, triglycerides) and CRP). Next, blood pressure readings will be made in duplicate.

Body weight will be assessed on a beam scale and body composition assessed using a Tanita scale based on bioelectrical impedance (BIA).

Subjects will then be instructed on how to complete 24-hour dietary recalls and estimate portion sizes and will complete a Brief Block FFQ on-site as well as a 7 day physical activity recall. At the close of visit 1, subjects will receive an individualized timetable for future study visits, and will agree to receive phone calls for 24-h dietary recalls (3 unannounced phone calls during 1 week in between study visits) and one physical activity recall without being given an exact date.

	Protocol Name:	Multi-level supermarket discounts of fruits and vegetables on intake and health
	Principal Investigator:	[name]
	Primary Contact Name/Contact Info:	[name] [contact] [name] [contact]
	Date Revised:	8/7/20
	Study Number:	HS#: 16-00407 GCO#: 16-1050

Subjects will be informed that there will be different discount levels (30, 15, 0%), and that those in the 0% discount group will receive a discount of 30% for 16 weeks after the study, beginning Week 57. The Allegiance-affiliated supermarket reward scan cards provided at visit 1 will be used to track purchases and to activate the discounts during the intervention period.

#### Study Visit 2-5; wk 8, 24, 40, 56 (Duration: ~30 min)

These visits will take place at the hospital or Quest Diagnostics during the final week of each period end-point (wk 8, 24, 40 and 56).

Each one of these visits will be preceded by a 12-hour overnight fast. After completing the morning questionnaire, the nurse will take body temperature, blood pressure readings and draw a blood sample. The same chemistry panel described for visit 1 will be ordered. Body weight and body composition will be assessed as described for visit 1 and a Brief Block FFQ will be completed either in-person or virtually using REDCap and a secure Zoom interface,

Subjects will receive, in paper if they wish, and e-mail format, a summary of foods and beverages available for discount during the study as well as a list of conditions to remain in the study. At each visit, subjects will be asked to present the Allegiance affiliate supermarket tag provided to them for use in the study. Staff will confirm that the number on the tag presented matches the tag number provided at Visit 1.

Finally, subjects will be reminded that in the weeks following these visits they will receive phone calls for 24-h dietary and physical activity recalls, without being given exact dates.

#### Study visit 2; wk 8 (Duration ~20 min)

In addition to the general chemistry panel, the blood draw will be used to assess carotenoids to reflect F&V intake (only if the participant is not currently taking vitamin A supplements).

At this study visit, they will be informed of their randomization into 1 of 3 discount level groups, stratified by gender within each grocery store. Subjects will receive, in paper, if they wish, and e-mail format, a summary of foods and beverages available for discount during the study as well as a list of conditions to remain in the study. Subjects will be asked to save their receipts if they believe they did not receive the expected discount, to bring to our attention (rather than to store staff or managers) at their next visit for possible reimbursement.

#### Study Visit 4; wk 40 (Duration: ~20 min)

addition to the general chemistry panel described for visit 2-5, the blood draw will be used to assess carotenoids to reflect F&V intake (only if the participant is not currently taking vitamin A supplements).

	Protocol Name:	Multi-level supermarket discounts of fruits and vegetables on intake and health
	Principal Investigator:	[name]
	Primary Contact Name/Contact Info:	[name] [contact] [name] [contact]
	Date Revised:	8/7/20
	Study Number:	HS#: 16-00407 GCO#: 16-1050

### Study Visit 5; wk 56 (Duration: ~ 30 min)

This visit will also include a confidential exit interview, either in-person or virtually using REDCap and a secure Zoom interface, with subjects (**Appendix G**) at the end of the study. The interview will follow after the final study payment, if possible, to decrease social desirability bias in responses. The interview will review compliance with the protocol, help detect any previous reporting bias, and obtain feedback about the subjects' experience (**Appendix H**). Although no deception is used in this protocol, a debriefing session will be used to review the purpose of the study and answer any questions subjects may have. General nutritional information will also be provided.

### Measures

**Food Purchasing Data:** Data will be recorded via the scan cards and transmitted by Allegiance electronically on a secured server. Purchases will be categorized by type, quantity, and price, and separated by study period (baseline, intervention, or follow-up). Gross dollars of discounted F&V will be obtained and further categorized, first by whether fruit or vegetable. Then, fruits will be further categorized as citrus, berries, melons, and lycopene/red (tomatoes, watermelon). Vegetables will be categorized as dark green leafy (kale), red/orange, legumes, starchy (green peas, corn), allicin/bulb (garlic, scallion). These additional subcategories will be considered as secondary outcomes. We will examine non-caloric beverages and categorize by diet sodas and bottled water. We also assess categories of food of high energy density (ED). ED is defined as kilocalories per unit weight (kcal/g). High ED foods tend to have more fat and sugar, e.g., packaged snack foods, whereas low ED foods consist mainly of F&V. There is no definitive consensus on what demarcates low or high ED [137], but a useful benchmark for low ED would be < 1 kcal/g and for high ED would be > 4 kcal/g. We will examine purchasing of food items > 4 kcal/g, including bakery, candies, ice cream, and salty snacks and categorize this data. We will examine purchases of specified high energy foods (including bakery goods) and processed snack foods (incl., confectionaries, salty snacks, ice cream).

**24-h Dietary Recalls (NDSR):** The 24-hour dietary recalls will be collected using Nutrition Data System for Research (NDSR), a computer-based software application developed at the University of Minnesota Nutrition Coordinating Center (NCC) that facilitates the collection of recalls in a standardized fashion. After all foods are coded and assigned weights, they will be reviewed, edited, and analyzed using the NDSR, which encompasses the USDA Food and Nutrient Database for Dietary Studies (FNDDS). The NDSR contains more than 11,100 food images and can handle the great majority of supermarket processed foods. It is adequate for characterizing intake for between-group comparisons, 3-day recalls will minimize intra-individual day-to-day variability and provide a better estimate of dietary intake. Energy and macronutrient content will be obtained from three NDSR dietary recalls by phone on randomly selected 2 weekdays and 1 weekend day, during the middle of each study period. 1-h recalls are less burdensome than food diaries and less likely to influence eating behavior, as it is without forewarning [151]. The NDSR is a fully computerized, interview-administered, validated, five-

	Protocol Name:	Multi-level supermarket discounts of fruits and vegetables on intake and health
	Principal Investigator:	[name]
	Primary Contact Name/Contact Info:	[name] [contact] [name] [contact]
	Date Revised:	8/7/20
	Study Number:	HS#: 16-00407 GCO#: 16-1050

step process. Subjects are guided through the previous 24-h to obtain food and beverage intake in five passes: pass 1 includes a quick list of foods and beverages consumed the previous day; pass 2 includes probe questions for foods forgotten during the quick list; pass 3 sorts foods chronologically and into eating occasions; pass 4 collects more details about the amount, preparation, and additions to the foods consumed; and pass 5 is a final review and probe for anything missed. The five-pass method provides multiple opportunities for subjects to remember and report additional foods and beverages. Special instructions and follow-up questions are incorporated. Subjects will be provided with food and beverage images via NDSR booklet materials to reduce error in estimating amounts. After all foods are coded and assigned weights, they will be reviewed, edited, and analyzed using NDSR which encompasses the USDA Food and Nutrient Database for Dietary Studies (FNDDS) and will provide weighted means for ED, calories, and macro- and micro-nutrient composition. (Duration: 15 min per phone recall)

**Dietary Measures:** The NDSR contains the great majority of supermarket food items and will provide an estimate of 24-h daily energy intake. For solid foods, we will calculate (g and serving sizes) high ED foods (> 4 kcal/g) and low ED foods (<1 kcal/g), mean energy density, as well as the daily fat content (g), a proxy for high calorie content. We will analyze F&V intake (g), which is the primary outcome measure (used to power the study). From the consumption of high ED foods, we will assess whether increased F&V intake displaces intake of high ED foods. Plasma carotenoids and Vitamin C will be used to corroborate the more subjective measure of 24-h dietary recall. In addition, the Brief Block Food Frequency Questionnaire (FFQ) will be administered to corroborate the dietary assessments.

**Physical Activity Measures:** Physical activity measures will be collected using the International Physical Activity Questionnaire (IPAQ) Short Last 7 Day Telephone Format. It is an open access questionnaire designed primarily for population surveillance of physical activity among adults. It has been developed and tested for use in adults (age range of 15-69 years). IPAQ assesses physical activity undertaken across a comprehensive set of domains including: leisure time physical activity, domestic and gardening activities, work related physical activity and transport related physical activity. The IPAQ short form asks about three specific types of activity undertaken in the four domains introduced above. The specific types of activity that are assessed are walking, moderate-intensity activities and vigorous-intensity activities. An additional indicator variable of time spent in sedentary activity is also included. Guidelines for Data Processing and Analysis of the IPAQ are available and will be followed. (5 min per phone call)

**Phone (or In-Store) Screener:** A baseline screener (**Appendix A**) will be used to obtain estimated height and weight and determine if subjects meet the basic eligibility criteria for the study as outlined in section 5b.

**Questionnaires and Interview:** A brief interview (Morning Questionnaire (**Appendix L**)) and four questionnaires will be completed virtually using REDCap and a secure Zoom interface during or close in time to visit 1- 5 including the Behavioral Checklist (**Appendix D**), Appetite Ratings (**Appendix E**),

	Protocol Name:	Multi-level supermarket discounts of fruits and vegetables on intake and health
	Principal Investigator:	[name]
	Primary Contact Name/Contact Info:	[name] [contact] [name] [contact]
	Date Revised:	8/7/20
	Study Number:	HS#: 16-00407 GCO#: 16-1050

Fruit, Vegetable, and Snack Food Liking (**Appendix F**), and Brief Block Food Frequency Questionnaire (**Appendix J**). The screening visit will include the Morning Questionnaire, Behavioral Checklist (**Appendix D**) and a Medical History Questionnaire (**Appendix M**).

**Morning Questionnaire:** Consists of two questions to ensure that the participant has fasted for 12h (Duration: < 1 min)

**Medical History Questionnaire:** will be used at Screening Visit to obtain additional medical history information. (Duration: 10 min)

**Income questionnaire (Appendix B)** will be used to obtain additional income information. This questionnaire will be emailed only prior to visit 1. (Duration: 5 min)

**Behavioral Checklist:** A brief structured interview will help ensure adherence, e.g., no change in smoking, diet, medications, etc. Deviations will be controlled for if imbalanced by group. This questionnaire will be completed at or close to the screening visit and during subsequent study visits. (Duration: 10 min)

**Appetite Ratings:** Visual Analogue Scales (VAS) will be used to rate hunger and satiety (**Appendix E**) on the 5 morning visits. Questions include “How hungry do you feel?”, “How full do you feel?”, and “How much is your desire to eat?” with anchors for “Extremely” and “Not at all” to help assess whether increases in F&V intake alters appetite. (Duration: 1 min)

**Fruit, Vegetable, and Snack Food Liking (Appendix F):** This measure contains ratings of 5 frequently eaten items from the categories of fruits, vegetables, and snack foods. Food preferences may change after exposure and eating behavior of F&V [160], with increases in F&V liking, which may help sustain the intervention effects. It has been shown that preference increases for previously disliked vegetables after 9-10 taste exposures [161]. Although the majority of this research has been in children, it may also occur in adults [162]. (Duration: 4 min)

**Brief Block Food Frequency Questionnaire (FFQ):** will be administered to corroborate the 24h-dietary recalls and purchasing data. (Duration: 15 minutes)

**Physical Assessments:** All anthropometric measures will be made in duplicate at wk 0, 8, 24, 40, 56 on S&R 11 in the patient examining room by trained research technicians blind to the subjects' group assignment. Subjects will be asked to use the bathroom to void and to remove footwear and empty pockets prior to measurement.

1. Height will be measured with a stadiometer (at Screening Visit only)

	Protocol Name:	Multi-level supermarket discounts of fruits and vegetables on intake and health
	Principal Investigator:	[name]
	Primary Contact Name/Contact Info:	[name] [contact] [name] [contact]
	Date Revised:	8/7/20
	Study Number:	HS#: 16-00407 GCO#: 16-1050

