### **Brief Summary of Research (250-400 words):**

Our objective is to test the effect of various supermarket discount levels on fruit and vegetable (F&V) and non-caloric beverage purchasing and consumption, as well as health outcomes. We will implement this economic intervention in a local supermarket chain to assess the effects of a 32-week intervention of fruit and vegetable (F&V) and non-caloric beverage discounts of 30%, 15%, and 0% (control group) on purchasing, dietary intake, and health outcomes, including body weight and composition, blood pressure, and biochemical markers of cardiovascular disease risk. The 32-week intervention will be preceded by an 8-week baseline and will have a follow-up period of 16 weeks. There will be no discounts in effect during the baseline and follow-up periods.

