### Specific Aims:

For the aims below, the first outcome (underlined) within each aim is primary, and the other outcomes are secondary.

**Primary Aim 1:** To investigate the effects of multi-level discounts on behavioral and health outcomes during the intervention period and their sustained effect during the follow-up period.

For greater price discounts ( $30\% > 15\% > 0\%$  group), we predict:

- a. *Purchasing Behaviors*
  - i. higher individual gross purchasing (i.e., price before discount) of F&V and non-caloric beverages
  - ii. reduced individual gross purchasing of less healthy, high energy dense (ED) highly processed foods (e.g., processed bakery items)
- b. *Consumption Behaviors*
  - i. higher individual F&V intake (g), the primary outcome measure (used to power the study), as assessed by 24-h dietary recalls and Brief Block Food Frequency Questionnaires (FFQ) (confirmed by biomarkers: plasma carotenoids and Vitamin C), as well as greater intake of non-caloric beverages
  - ii. decreased high energy-dense (ED) food intake (g), lower total fat intake (g), and lower daily energy intake (kcal)
- c. *Health Outcomes*
  - i. lower body weight (kg) and BMI ( $\text{kg}/\text{m}^2$ ), lower % body fat
  - ii. improved metabolic syndrome risk factors (fasting glucose, blood lipids, blood pressure)

	Protocol Name:	Multi-level supermarket discounts of fruits and vegetables on intake and health
	Principal Investigator:	[name]
	Primary Contact Name/Contact Info:	[name] [contact] [name] [contact]
	Date Revised:	8/7/20
	Study Number:	HS#: 16-00407 GCO#: 16-1050

**Primary Aim 2:** To investigate the effects of income as a moderator of outcome measures.

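### The protocol's derivation rule for F&V purchasing is limited to discounted items, while Aim 1a(i) covers all F&V; if the discount list is partial, switching between F&V products would count as extra purchasing.

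*Protocol*

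**What the plan says.** Under Specific Aims, Primary Aim 1 a(i) of the protocol predicts "higher individual gross purchasing (i.e., price before discount) of F&V and non-caloric beverages". Nothing there limits the outcome to items that carry a discount.

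The Food Purchasing Data paragraph (section 5f, Measures) is the only place that says how F&V purchasing is computed. It first has all scan-card purchases classified by type, quantity and price within each study period. It then gives the rule for F&V: "Gross dollars of discounted F&V will be obtained and further categorized, first by whether fruit or vegetable". The fruit and vegetable subcategories, named as secondary outcomes, are subdivisions of that figure. The sentences on non-caloric beverages and high energy-dense foods carry no such limit.

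The word discounted is not defined for the control arm or for the periods without discounts. The Brief Summary states: "There will be no discounts in effect during the baseline and follow-up periods". Participants are given "a summary of foods and beverages available for discount during the study" (Study Visit 2-5), but the documents do not say whether that summary takes in all F&V sold or only some. The SAP defines no purchasing outcome, so it does not settle the matter.

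**The concern.** The aim and the derivation rule describe two different quantities unless every F&V item sold is on the discount list. If some are not, only the 15% and 30% arms have a discount-driven reason to replace unlisted F&V with listed F&V. The rule would count what is gained on the list and leave out what is lost off it. Controls have no such incentive, so the difference would go into the between-arm contrast. If switching grows with the depth of the discount, it would also resemble the graded response that the aim predicts.

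At stake are the purchasing outcome under Aim 1a and the planned regression of F&V demand on discount level (Economic Analysis, in Background Significance). In that regression, switching between products would be read as added demand for F&V. The protocol says its main objective is to encourage F&V subsidies at government level, so the distinction between more F&V and different F&V matters for how the result is used.

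**Working it through.** The plan gives no figure to reproduce; this is a question of definition, followed by illustrative arithmetic.

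**Step 1: what the rule can mean.** Two readings are possible: items sold at a reduced price, or items on the discount list whatever price was paid. The first would leave most arm-by-period cells empty and is set aside under the objection. The second can be computed in every arm and period and is the plausible one.

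**Step 2: does the list cover all F&V?** The documents leave this open.
- Pointing to a partial list: the preliminary study discounted only a selection of F&V; participants here receive a summary of eligible items; and the qualifier in the rule would be unnecessary if all F&V were eligible.
- Pointing to full coverage: the Brief Summary and the Research Question describe discounts on F&V without any such restriction.

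**Step 3: size of the switching artefact.** Let *s* be the share of baseline F&V dollars (pre-discount) spent on unlisted items, and *m* the fraction of that spending which moves to listed items. Hold total F&V dollars constant. Listed spending goes from (1 − *s*) to (1 − *s*) + *s·m*, so

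apparent rise = *s·m* / (1 − *s*).

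The documents give neither *s* nor *m*; both are assumptions.

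| Unlisted share *s* | *m* = 0.25 | *m* = 0.50 |
|---|---|---|
| 0 (list covers all F&V) | 0% | 0% |
| 0.10 | 0.025/0.90 = 2.8% | 0.050/0.90 = 5.6% |
| 0.20 | 0.050/0.80 = 6.2% | 0.100/0.80 = 12.5% |
| 0.30 | 0.075/0.70 = 10.7% | 0.150/0.70 = 21.4% |

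As a worked case, assume $20 of F&V a week with *s* = 0.20 and *m* = 0.50. Listed spending goes from $16 to $18 and unlisted spending from $4 to $2. The rule reports a rise of 2/16 = 12.5%, while total F&V stays at $20.

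**Step 4: the same case under the aim's definition.** Counting all F&V at pre-discount price, the change is 0% for any *s* and *m*.

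**Step 5: can the aim's definition be computed?** Yes. All purchases on the card are classified by type, quantity and price, and the same paragraph uses the data for high energy-dense foods, which are not discounted. The scan data therefore reach beyond the discounted items.

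**The case against.** The strongest reply is that this is loose wording and not a biased analysis. Aim 1a(i) already defines the outcome without restriction, the scan data allow it to be computed, and the protocol never says that the discounted subtotal replaces it. The demand regression is likewise described as concerning F&V, not discounted F&V. Nor do the documents show that the list is partial: the restriction to a selection appears only in the account of the preliminary study, and participants would need a summary sheet anyway, for instance to know which beverages qualify. With full coverage the artefact is exactly zero.

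Much of this stands. The bias is conditional, and its size rests on assumed inputs. What does not fall away is the mismatch: the only written derivation rule names a narrower quantity than the aim. That total F&V can be computed shows that the correction is cheap, not that the rule already asks for it.

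A reader might go further and infer that the outcome is zero by rule for controls throughout and for every arm at baseline and follow-up, because no discount applies there. That would leave only 2 of 9 arm-by-period cells non-zero and make any contrast positive by construction. The documents do not support this reading. The same paragraph separates purchases by baseline, intervention and follow-up, which would be pointless if two of the three were empty. Gross is defined as the price before discount, which allows arms with different discounts to be compared. And the preliminary study, with a discount on selected F&V, still reported control-group F&V purchasing and a baseline F&V share of 7% of total purchasing in the discount group.

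A reader might also extend the point to non-caloric beverages. The Measures text does not limit those to discounted items, so there is nothing to correct there.

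**Conclusion.** The point holds as a mismatch of definitions with a conditional bias. Aim 1a(i) and the Food Purchasing Data rule need to be reconciled. If the discount list omits some F&V, the rule as written would overstate the effect of the discounts on F&V purchasing by *s·m*/(1 − *s*): about 3% to 21% for assumed unlisted shares of 10% to 30% with a quarter to a half switching at constant total spending. If the list covers all F&V, the overstatement is 0%. The documents do not say which case applies, so an established bias towards the discount arms should not be claimed.

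The reach is limited. Specific Aims says that "the first outcome (underlined) within each aim is primary, and the other outcomes are secondary", and purchasing is listed first under Aim 1, but the same section names F&V intake in grams as the primary outcome measure used to power the study. The SAP's primary outcomes are intake and body weight. None of these depends on the purchasing rule.

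**What to change.** In Food Purchasing Data, and in the SAP if purchasing is to be reported, define the F&V purchasing outcome as pre-discount dollars of all F&V bought on the study card, whether or not the item is on the discount list, in every arm and every study period. Report the listed-item subtotal as a secondary breakdown, using the same fixed list in all arms and periods. Base the fruit and vegetable subcategories and the demand regression on the all-F&V figure. State what share of F&V the discount list covers; if it is all of it, say so, and the two figures coincide.

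The cost is a sentence or two of wording and the coding of a longer set of F&V product codes. No new data collection is needed, because the scan records already classify purchases by type, quantity and price.
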